## Software

Sample size was based on Rosner's method calculated by Gpower 3.0.10. All of the obtained data will be collected, statistically analyzed and presented in the form of tables, graphs and charts using the IBM Statistical Package for Social Science (SPSS) software version 20.0.

## **Eligibility Criteria**

The criteria for including patients are as follows:

[figure not shown]
### **Inclusion criteria**

- Adult patients ranging from 20-40 years.
- Adequate bone beyond teeth apices without jeopardizing any anatomical structure.
- Non-restorable mandibular molar teeth.
- Available bone with adequate width and buccolingual dimensions.
- Peri-implant bone defect should be 2mm or lesser.

### **Exclusion criteria**

- Smokers.
- Medically compromised patients like uncontrolled diabetes and coagulation disorders.
- Tooth with periapical pathosis or bony defects.

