## Summary Statement

Sample size was estimated assuming 5% alpha error and 80% study power. Tsallarico et al reported that the mean Implant Stability Quotient (ISQ) values at baseline for ultra-wide implants was  $65.5 \pm 7.6$  and  $78.8 \pm 2.8$  after 6 months of implant placement. The sample will be stratified by gender into two groups. Sample size was calculated to be 5 patients per group, increased to 6 patients to make up for loss to follow up. Total sample size = number per group  $\times$  number of groups =  $6 \times 2 = 12$  patients.

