## **Phases**

### **I. Preoperative Phase**

#### ***1- History***

##### **a) Personal history**

Full personal data in details is required; including name, age, gender, occupation, address, telephone number. Also, the telephone number of relatives and companions.

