##### **b) Past medical history**

History of any medical condition like diabetes, hypertension, drug allergy or any medications.

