## ***3- Radiographic examination***

Cone-Beam Computed Tomography (CBCT) to evaluate the condition and anatomy of tooth, presence of any periapical pathology and for treatment planning.

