### **Postoperative medication**

They will be advised to take the prescribed medications, which include:

- Amoxicillin 875mg + Clavulanic acid 125mg \* every 12 hours for 7 days.
- Non-Steroidal Anti Inflammatory drugs\*\* every 8 hours for 4 days.
- Chymotrypsin +Trypsin 300 E.A.U\*\*\* every 8 hours for 5 days
- 0.12% chlorhexidine mouth wash\*\*\*\* 3 times daily for 2 weeks.
- Sutures will be removed after one week from surgery.

---

\* Augmentin: GalaxoSmithKline,UK

\*\* Cataflam: Diclofenac potassium 50mg: Novartis. Switzerland

\*\*\* Alphinern: Chemotrypsin 300 E.A.U (14microkatal) +Trypsin 300 E.A.U (5microkatal): Amoun Pharmaceutical Co. S.A.E

\*\*\*\* Hexitol: Chlorhexidine 125mg/100ml concentration 0.125%: Arabic drug company, ADCO

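### Pregnancy is not named as an exclusion or a history question in the available text, although women aged 20 to 40 receive a diclofenac course and CBCTs up to month 9

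*Combined protocol and SAP*

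**What the plan says.** **Who is enrolled.** The Inclusion criteria admit "Adult patients ranging from 20-40 years", with no restriction by sex. The Summary Statement says "The sample will be stratified by gender into two groups" and then "Sample size was calculated to be 5 patients per group, increased to 6 patients to make up for loss to follow up", so the plan is for 6 women and 6 men.

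**Who is kept out.** The Exclusion criteria have three lines: smokers, a general medical line ("Medically compromised patients like uncontrolled diabetes and coagulation disorders"), and a line on disease or defects at the tooth site.

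**What is asked.** The personal history reads "Full personal data in details is required; including name, age, gender, occupation, address, telephone number". The medical history reads "History of any medical condition like diabetes, hypertension, drug allergy or any medications". The remaining items are dental history and chief complaint. None of them names pregnancy.

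**What every participant receives.** Postoperative medication includes an NSAID, footnoted as diclofenac potassium 50 mg, taken "every 8 hours for 4 days". Before surgery there is a planning scan: "Cone-Beam Computed Tomography (CBCT) to evaluate the condition and anatomy of tooth". The Radiographic Evaluation section then schedules a CBCT directly after surgery, at 6 months and at 9 months, to assess bone density and crestal bone loss.

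**The concern.** The protocol recruits women of childbearing age and prescribes both a drug course and repeated X-ray imaging. The text that can be read does not tell the investigator to find out whether a woman is pregnant, or what to do if she is.

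Two situations are left open:

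- **Pregnancy at enrolment.** The planning CBCT, the immediate postoperative CBCT and the diclofenac course could all be given.
- **Pregnancy that begins during follow-up.** A history taken at enrolment cannot detect it, and no check is named before the scans at months 6 and 9. The stated purpose of those scans is to measure study outcomes, so the protocol itself should say when they are not taken.

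What is at stake is patient safety. The power of the trial is not in question.

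**Working it through.** This point is decided by reading. The arithmetic only counts exposures.

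**1. Is pregnancy mentioned anywhere in the readable text?** No. The Exclusion criteria, the four history items, the clinical and radiographic examination, the operative and postoperative sections, Participant Safety, Follow Up policy and the study schedule contain no reference to pregnancy, pregnancy testing, lactation or contraception.

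**2. Could the open wording cover it?** Both the medical exclusion and the medical history line give examples and not closed lists. The examples for exclusion are uncontrolled diabetes and coagulation disorders. Those for history are diabetes, hypertension, drug allergy and medications. A healthy pregnancy is not naturally a case of being medically compromised. A clinician may ask about it, but the text does not require the question.

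**3. Does imaging really run to month 9?** The Follow Up policy speaks of 6 months. The Clinical follow-up phase, the Radiographic Evaluation section and the Duration of Study table all run to month 9, and the budget pays for three CBCTs per patient. The month 9 scan is therefore taken as planned.

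**4. Exposure counts.**

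- Plan's total sample: 6 per group × 2 groups = 12.
- Plan's CBCT budget: 3 × 12 = 36 scans, and 36 × 400 = 14,400 L.E., which matches the budget table.
- Trial-scheduled CBCTs in women: 3 × 6 = 18, which is 18/36 = 50% of the total. For any other number of women *w*, the count is 3 × *w*.
- NSAID doses per participant: 24/8 = 3 per day, and 3 × 4 days = 12.

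**5. When would a question have to be asked?** The exposures fall at four times.

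| Exposure | Time | Question needed |
|---|---|---|
| Planning CBCT | before surgery | before this scan |
| Postoperative CBCT and diclofenac | day of surgery and next 4 days | on the day of surgery |
| CBCT | month 6 | before this scan |
| CBCT | month 9 | before this scan |

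The interval between the planning CBCT and surgery is not stated, so the first question cannot be assumed to hold on the day of surgery.

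**6. Data cost of omitting a scan.** One participant of 12 is 1/12 = 8.3% of the radiographic data at that visit.

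**The case against.** The strongest reply has three parts.

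**The lists are illustrative.** In a short protocol run by a hospital oral surgery department, the open medical clauses leave room for clinical judgement, and a careful operator may well ask. This stands in part. It does not make the question a requirement, and it does nothing for a pregnancy that begins after enrolment.

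**Some material cannot be seen.** A figure sits under Eligibility Criteria, and the consent pages are not available. Pregnancy could be named in either. This limits the point to the readable text. The written inclusion and exclusion lists that follow the figure do look complete.

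**The documents show no harm.** They give no CBCT dose, fetal risk or pregnancy rate. This stands, and most strongly for the scans at months 6 and 9, where jaw imaging is the only exposure. The number of pregnant women among 6 may be zero.

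Two stronger readings are tempting and are not supported. A reader might take the share of scans in women as a measure of risk, or add the planning scans to enlarge it. The count covers all planned women, pregnant or not. The planning CBCT serves treatment planning and lies outside the three budgeted scans, so it should not be pooled with the trial-scheduled ones. A reader might also infer that one preoperative check deals with everything up to and including surgery. A check on the day of surgery comes after the planning CBCT, and a check before the planning CBCT covers surgery only if the unstated interval is short.

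**Conclusion.** The point holds for the text available. Followed literally, the eligibility rules admit a healthy pregnant woman to a 12-dose diclofenac course and to the scheduled CBCTs, and no check precedes the later scans. If the planned 6 women are enrolled, 18 of the 36 trial-scheduled CBCTs are in women. That figure assumes the gender groups fill as planned and the month 9 scan takes place. No probability or size of harm is claimed.

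This is a change worth making for patient safety. It is not a flaw in the sample size calculation or the analysis method, and neither is affected.

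**What to change.** 1. **Exclusion criteria:** add pregnancy as a named exclusion.
2. **Past medical history:** add a pregnancy question, asked before the planning CBCT and again on the day of surgery, before the postoperative CBCT and the NSAID course.
3. **Radiographic Evaluation:** add a sentence requiring the question before the month 6 and month 9 CBCTs, with the scan deferred or omitted if the answer is yes.

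The cost is one exclusion line, one history item and one sentence. In practice it means four questions per enrolled woman, two of them during follow-up (2 × 6 = 12 follow-up questions with 6 women). There may be a few more screening failures. A deferred scan would be late, and each omitted scan loses 8.3% of participants from the bone density and crestal bone loss data at that visit. A rule set in advance is better than an unplanned decision at the visit.

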## Study Design

## **Materials**

1. (Dentium Superline implant, diameter 7mm, South Korea). \*
2. Osstell.\*\*
3. Physiodispenser\*\*\*

## **Phases**

### **I. Preoperative Phase**

#### ***1- History***

##### **a) Personal history**

Full personal data in details is required; including name, age, gender, occupation, address, telephone number. Also, the telephone number of relatives and companions.

##### **b) Past medical history**

History of any medical condition like diabetes, hypertension, drug allergy or any medications.

##### **c) Past dental history**

History of periodontal disease, badly destructed teeth, swelling, trauma, failed restorations, any oral pathology and past dental experiences.

##### **d) Chief complaint**

The patient's chief complaint, desire and expectations will be documented.

---

\*Superline,Dentium Co,Doublethread,S.L.A surface (sandblasted with large grit and Acid etched),Korea

\*\* Osstell: Osstell, Sweden

\*\*\*(COXO | C-SAILOR IMPLANT MOTOR),china.

## ***2- Clinical examination***

Soft tissue will be examined for any suppuration or discharge, swelling or tooth mobility.

## ***3- Radiographic examination***

Cone-Beam Computed Tomography (CBCT) to evaluate the condition and anatomy of tooth, presence of any periapical pathology and for treatment planning.

## **II. Surgical Phase**

### ***1- Preoperative patient preparation***

To control infection, antibiotic prophylaxis will be 1 gm amoxicillin+clavulanate sixty minutes before operation, according to the (INFECTIOUS DISEASES SOCIETY of AMERICA) guidelines.

### ***2- Operative procedure***

- Surgery will be performed under local anesthesia (Mepecaine-L) with 1:20000 adrenaline.
- Atraumatic tooth extraction of molar teeth without any flaps or bone removal.
- Pilot hole will be performed in inter-radicular septum following root removal.
- Osteotomy preparation will be completed up to the planned diameter of the implant, which was based on the socket dimensions, followed by implant insertion.

- The implant shoulder should be ensured to be seated 2mm below the lowest point of buccal wall and 2mm distance from the buccal wall.
- A healing abutment will be then connected to the implant and soft tissue adaptation as well as void closure will be obtained with suturing and hemostatic collagen sponge at the level of the healing abutment.

### ***3- Postoperative care***

- Patients will be given comprehensive oral hygiene care and postoperative instructions, including;
  - Not to rinse for 24 hours after surgery.
  - Cold fomentation for 24 hours only postoperatively.
  - Soft diet, high protein, high calorie diet and fluids for 2 weeks postoperatively.

### **Postoperative medication**

They will be advised to take the prescribed medications, which include:

- Amoxicillin 875mg + Clavulanic acid 125mg \* every 12 hours for 7 days.
- Non-Steroidal Anti Inflammatory drugs\*\* every 8 hours for 4 days.
- Chymotrypsin +Trypsin 300 E.A.U\*\*\* every 8 hours for 5 days
- 0.12% chlorhexidine mouth wash\*\*\*\* 3 times daily for 2 weeks.
- Sutures will be removed after one week from surgery.

---

\* Augmentin: GalaxoSmithKline,UK

\*\* Cataflam: Diclofenac potassium 50mg: Novartis. Switzerland

\*\*\* Alphinern: Chemotrypsin 300 E.A.U (14microkatal) +Trypsin 300 E.A.U (5microkatal): Amoun Pharmaceutical Co. S.A.E

\*\*\*\* Hexitol: Chlorhexidine 125mg/100ml concentration 0.125%: Arabic drug company, ADCO

#### ***4- Clinical follow-up phase***

Patients will be followed-up both clinically and radiographically for 9 months.

##### **a) Clinical Evaluation**

###### **1- Postoperative pain.**

- It will be recorded for each patient after 48 hrs postoperatively, then after one week through a 10-point Visual Analogue Scale (VAS) from 0 to 10.
- (0-1= None, 2-4= Mild, 5-7= Moderate, 8-10= Severe).

###### **2- Postoperative swelling.**

- It will be recorded for each patient after 48 hours postoperatively, then after one week through a 10-point scale with 4 parameters will be used.
- None (no swelling), light (intraoral, localized to the treated area), moderate (extraoral swelling localized to the treated area), and severe (extraoral swelling extending beyond the treated area).

###### **3- Implant stability.**

- It will be measured by implant stability meter (Osstell™) immediately postoperative and at 6 months.

###### **4- Peri-implant probing depth.**

- Pocket probing on dental implants should be conducted with a light force (approximately 0.25 N); peri-implant pocket depths should be  $\leq 5$  mm.

**b) Radiographic Evaluation**

Immediately postoperative, after 6 months and after 9 months CBCT will be requested in order to evaluate:

- 1- Peri-implant bone density
- 2- Crestal bone loss

**III. Prosthetic phase**

After 6 months of integration, the implant was restored with a cemented retained crown.

## **STATISTICAL ANALYSIS**

All of the obtained data will be collected, statistically analyzed and presented in the form of tables, graphs and charts using the IBM Statistical Package for Social Science (SPSS) software version 20.0.

# **ETHICAL CONSIDERATIONS**

## **Participant Safety**

The study subjects will receive both oral and written information about the benefits and risks of the interventions, also about the gained advantages compared to the conventional method which are reduced treatment plan time, less procedure steps and placement of the implant fixture in an optimal axial position threats.

## **Follow Up policy**

The patients will be followed up for 6 months in the outpatient clinic of Oral and Maxillofacial Surgery Department, Faculty of Dentistry. All patients' personal information will be recorded, and a direct contact with the patient and his or her relatives will be established using telephone number in order to ensure ease of recall and to provide keen and up to date follow up.

## **Informed Consent**

All patients will sign an Informed Consent Form before undergoing the operation to ensure and confirm their understanding of the outcome of the operation and the risks they might be subjected to during the intervention.

## **Research Ethics Committee approval**

The clinical part of the study will be performed after gaining the ethical clearance from the Research Ethics Committee, Faculty of Dentistry, Alexandria University.

## DURATION OF STUDY

**Estimated Time:** 12 months.

Tasks/Duration	1st day	1st week	1st Month	4th Month	6th Month	9th Month	9th – 12th Month
Surgical Procedure	√						
Clinical Evaluation		√	√	√	√	√	
Radiographic Evaluation	√				√	√	
Data Collection							√
Data Analysis							√
Writing Manuscript							√

## **ESTIMATED BUDGET**

**Total Budget:**

Item	Quantity/patient	Cost /L.E	Total
CBCT	3x12	400	14400
Armamentarium		3000	3000
Implant	1x12	2400	28800
Total			46200

## **PROBLEMS ANTICIPATED**

- Microbial interference with osteointegration.
- Failure to recall the patient for follow up (Follow up dropout).

## **PUBLICATION POLICY**

The study will be submitted for either national or international journals for publication.

- [name].
- [name]. [name].
- [name] [name].

